#### **9.4 Compliance with Trial Registration and Results Posting Requirements**

Under the terms of the Food and Drug Administration Modernization Act (FDAMA) and the Food and Drug Administration Amendments Act (FDAAA), the Sponsor of the trial is solely responsible for determining whether the trial and its results are subject to the requirements for submission to the Clinical Trials Data Bank, <http://www.clinicaltrials.gov>. Information posted will allow subjects to identify potentially appropriate trials for their disease conditions and pursue participation by calling a central contact number for further information on appropriate trial locations and trial site contact information.

#### **9.5 Quality Management System**

By signing this protocol, the Sponsor agrees to be responsible for implementing and maintaining a quality management system with written development procedures and functional area standard operating procedures (SOPs) to ensure that trials are conducted and data are generated, documented, and reported in compliance with the protocol, accepted standards of Good Clinical Practice, and all applicable federal, state, and local laws, rules and regulations relating to the conduct of the clinical trial.

#### **9.6 Data Management**

##### **Data Collection Instruments**

The Investigator will prepare and maintain adequate and accurate source documents designed to record all observations and other pertinent data for each subject treated with the study drug.

Study personnel at each site will enter data from source documents corresponding to a subject's visit into the protocol-specific paper Case Report Forms (CRFs) when the information corresponding to that visit is available. Subjects will not be identified by name in the study database or on any study documents to be collected by the Sponsor (or designee), but will be identified by a subject ID number and initials.

If a correction is made on a CRF, the study staff member will line through the incorrect data, write in the correct data and initial and date the change.

The Investigator is responsible for all information collected on subjects enrolled in this study. All data collected during the course of this study must be reviewed and verified for completeness and accuracy by the Investigator. By signing this protocol, the investigator acknowledges that his/her electronic signature is the legally binding equivalent of a written signature. By entering his/her electronic signature, the investigator confirms that all recorded data have been verified as accurate.

Detailed information regarding Data Management procedures for this protocol will be provided by the Sponsor.

### **Data Management Procedures**

The data will be entered into a validated database. The Data Management group will be responsible for data processing, in accordance with procedural documentation. Database lock will occur once quality assurance procedures have been completed.

All procedures for the handling and analysis of data will be conducted using good computing practices meeting FDA guidelines for the handling and analysis of data for clinical trials.

### **Data Quality Control and Reporting**

After data have been entered into the study database, a system of computerized data validation checks will be implemented and applied to the database on a regular basis. Query reports (Data Clarification Requests) pertaining to data omissions and discrepancies will be forwarded to the Investigators and study monitors for resolution. The study database will be updated in accordance with the resolved queries. All changes to the study database will be documented.

### **Archival of Data**

The database is safeguarded against unauthorized access by established security procedures; appropriate backup copies of the database and related software files will be maintained.

At critical junctures of the protocol (e.g., production of interim reports and final reports), data for analysis is locked and cleaned per established procedures.

### **Availability and Retention of Investigational Records**

The Investigator must make study data accessible to the monitor, other authorized representatives of the Sponsor (or designee), IRB/IEC, and Regulatory Agency (e.g., FDA) inspectors upon request. A file for each subject must be maintained that includes the signed Informed Consent, HIPAA Authorization and Assent Form and copies of all source documentation related to that subject. The Investigator must ensure the reliability and availability of source documents from which the information on the CRF was derived.

All study documents (patient files, signed informed consent forms, copies of CRFs, Study File Notebook, etc.) must be kept secured for a period of two years following marketing of the investigational product or for two years after centers have been notified that the IND has been discontinued. There may be other circumstances for which the Sponsor is required to maintain study records and, therefore, the Sponsor should be contacted prior to removing study records for any reason.

## **Monitoring**

Monitoring visits will be conducted by representatives of the Sponsor according to the U.S. CFR Title 21 Parts 50, 56, and 312 and ICH Guidelines for GCP (E6). By signing this protocol, the Investigator grants permission to the Sponsor (or designee), and appropriate regulatory authorities to conduct on-site monitoring and/or auditing of all appropriate study documentation.

## **Subject Confidentiality**

In order to maintain subject confidentiality, only a subject number and subject initials will identify all study subjects on CRFs and other documentation submitted to the Sponsor. Additional subject confidentiality issues (if applicable) are covered in the Clinical Study Agreement.

## **9.7 Data and Safety Monitoring Committee (DSMC)**

The Georgetown Lombardi Comprehensive Cancer Center will be responsible for the data and safety monitoring of this multi-site trial. As this study is an investigator initiated Phase II study utilizing an FDA approved drug for which the PI does not hold the IND it is considered a moderate risk study which requires real-time monitoring by the PI and study team and semi-annual reviews by the LCCC Data and Safety Monitoring Committee (DSMC).

The Principal Investigator and the Co-Investigators will review the data including safety monitoring at their weekly institution based disease group meetings and on monthly disease group teleconferences.

All Severe Adverse Events (SAEs) are required to be reported to the IRB. Based on SAEs, the IRB retains the authority to suspend further accrual pending more detailed reporting and/or modifications to further reduce risk and maximize the safety of participating patients.

Progress on the trial and the toxicities experienced will be reviewed by the LCCC Data and Safety Monitoring Committee every 6 months from the time the first patient is enrolled on the study. Results of the DSMC meetings will be forwarded to the IRB with recommendations regarding need for study closure.

DSMC recommendations should be based not only on results for the trial being monitored as well as on data available to the DSMC from other studies. It is the responsibility of the PI to ensure that the DSMC is kept apprised of non-confidential results from related studies that become available. It is the responsibility of the DSMC to determine the extent to which this information is relevant to its decisions related to the specific trial being monitored.

A written copy of the DSMC recommendations will be given to the trial PI and the IRB. If the DSMC recommends a study change for patient safety or efficacy reasons the trial PI must act to implement the change as expeditiously as possible. In the unlikely event that the trial PI does not concur with the DSMC recommendations, then the LCCC Associate Director of Clinical Research must be informed of the reason for the disagreement. The trial PI, DSMC

Chair, and the LCCC AD for Clinical Research will be responsible for reaching a mutually acceptable decision about the study and providing details of that decision to the IRB. Confidentiality must be preserved during these discussions. However, in some cases, relevant data may be shared with other selected trial investigators and staff to seek advice to assist in reaching a mutually acceptable decision.

If a recommendation is made to change a trial for reasons other than patient safety or efficacy the DSMC will provide an adequate rationale for its decision. If the DSMC recommends that the trial be closed for any reason, the recommendation will be reviewed by the Associate Director for Clinical Research at G-LCCC. Authority to close a trial for safety reasons lies with the IRB, with the above described input from DSMC and the AD for Clinical Research.

## **10.7 Publications**

This trial is intended for publication, even if terminated prematurely. Publication may include any or all of the following: posting of a synopsis online, abstract and/or presentation at a scientific conference, or publication of a full manuscript.

Authors of the primary results manuscript will be provided the complete results from the Clinical Study Report, subject to the confidentiality agreement. When a manuscript is submitted to a biomedical journal, the Sponsor's policy is to also include the protocol and statistical analysis plan to facilitate the peer and editorial review of the manuscript. If the manuscript is subsequently accepted for publication, the Sponsor will allow the journal, if it so desires, to post on its website the key sections of the protocol that are relevant to evaluating the trial, specifically those sections describing the trial objectives and hypotheses, the subject inclusion and exclusion criteria, the trial design and procedures, the efficacy and safety measures, the statistical analysis plan, and any amendments relating to those sections. The Sponsor reserves the right to redact proprietary information.

For multicenter trials, subsequent to the multicenter publication (or after public disclosure of the results online at [www.clinicaltrials.gov](http://www.clinicaltrials.gov) if a multicenter manuscript is not planned), an investigator and his/her colleagues may publish their data independently. In most cases, publication of individual trial site data does not add value to complete multicenter results, due to statistical concerns. In rare cases, publication of single trial site data prior to the main paper may be of value. Limitations of single trial site observations in a multicenter trial should always be described in such a manuscript.

Authorship credit should be based on 1) substantial contributions to conception and design, or acquisition of data, or analysis and interpretation of data; 2) drafting the article or revising it critically for important intellectual content; and 3) final approval of the version to be published. Authors must meet conditions 1, 2 and 3. Significant contributions to trial execution may also be taken into account to determine authorship, provided that contributions have also been made to all three of the preceding authorship criteria. Although publication planning may begin before conducting the trial, final decisions on authorship and the order of authors' names will be made based on participation and actual contributions to the trial and

writing, as discussed above. The first author is responsible for defending the integrity of the data, method(s) of data analysis and the scientific content of the manuscript.

The Sponsor must have the opportunity to review all proposed abstracts, manuscripts or presentations regarding this trial 45 days prior to submission for publication/presentation. Any information identified by the Sponsor as confidential must be deleted prior to submission; this confidentiality does not include efficacy and safety results. Sponsor review can be expedited to meet publication timelines

## **11.0 APPENDICES**

### **11.1 Common Terminology Criteria for Adverse Events V4.03 (CTCAE)**

The descriptions and grading scales found in the revised NCI Common Terminology Criteria for Adverse Events (CTCAE) version 4.03 will be utilized for adverse event reporting. (<http://ctep.cancer.gov/reporting/ctc.html>)

## 11.2 MM Diagnostic Criteria

Durie, Seminars in Oncology, Vol 13, No 3 (September), 1986: pp300-309:

### 1. Criteria for Diagnosis of Multiple Myeloma

#### Major criteria

- I. Plasmacytoma on tissue biopsy.
- II. Bone marrow plasmacytosis with >30% plasma cells.
- III. Monoclonal globulin spike on serum electrophoresis exceeding 3.5 g/dL for IgG peaks or 2.0 g for IgA peaks,  $\geq 1.0 \text{ g/24 h}$  of  $\kappa$  or  $\lambda$  light chain excretion on urine electrophoresis in the absence of amyloidosis.

#### Minor criteria

- a. Bone marrow plasmacytosis with 10% to 30% plasma cells.
- b. Monoclonal globulin spike present, but less than the levels defined above.
- c. Lytic bone lesions.
- d. Normal IgM <50 mg, IgA <100 mg, or IgG <600 mg/dL.

Diagnosis will be confirmed when any of the following features are documented in symptomatic patients with clearly progressive disease. The diagnosis of myeloma requires a minimum of one major + one minor criterion or three minor criteria that must include a + b

1. I + b, I + c, I + d (I + a not sufficient)
2. II + b, II + c, II + d.
3. III + a, III + c, III + d.
4. a + b + c, a + b + d.

### 2. Criteria for Monoclonal Gammopathy of Undetermined Significance (MGUS), Indolent Myeloma and Smoldering Myeloma (Stage I or IIa)

#### i. MGUS

- I. Monoclonal gammopathy
- II. M component level  
IgG  $\leq 3.5 \text{ g/dL}$   
IgA  $\leq 2.0 \text{ g/dL}$   
BJ  $\leq 1.0 \text{ g/24 h}$
- III. Bone marrow plasma cells <10%
- IV. No bone lesions
- V. No symptoms

ii. Indolent myeloma: Criteria as for myeloma (I above) with the following limitations:

- I. No bone lesions or only limited bone lesions ( $\leq 3$  lytic lesions); no compression fractures
- II. M component levels
  - a. IgG  $< 7 \text{ g/dL}$
  - b. IgA  $< 5 \text{ g/dL}$
- III. No symptoms or associated disease features
  - a. Performance status  $> 70\%*$
  - b. Hemoglobin  $> 10 \text{ g/dL}$
  - c. Serum calcium: normal
  - d. Serum creatinine  $< 2.0 \text{ mg/dL}$
  - e. No infections

Smoldering Myeloma: Criteria as for indolent myeloma with additional constraints:

- I. There must be no demonstrable bone lesions
- II. Bone marrow plasma cells  $\geq 10\% \leq 30\%$

### 11.3 International Staging System

Greipp PR et al, Journal of Clinical Oncology 2005, May 20:23 (15): 3412-20.

Stage	Criteria	Median survival (mos)
I	Serum Beta-2 microglobulin <3.5 mg/dL AND Albumin >3.5 mg/L	62
II	Neither I or III	45
III	Serum Beta-2 microglobulin >5.5 mg/L	29

#### 11.4 ECOG Performance Status

Grade	Description
0	Normal activity. Fully active, able to carry on all pre-disease performance without restriction.
1	Symptoms, but ambulatory. Restricted in physically strenuous activity, but ambulatory and able to carry out work of a light or sedentary nature (e.g., light housework, office work).
2	In bed <50% of the time. Ambulatory and capable of all self-care, but unable to carry out any work activities. Up and about more than 50% of waking hours.
3	In bed >50% of the time. Capable of only limited self-care, confined to bed or chair more than 50% of waking hours.
4	100% bedridden. Completely disabled. Cannot carry on any self-care. Totally confined to bed or chair.
5	Dead.

\* As published in Am. J. Clin. Oncol.: *Oken, M.M., Creech, R.H., Tormey, D.C., Horton, J., Davis, T.E., McFadden, E.T., Carbone, P.P.: Toxicity And Response Criteria Of The Eastern Cooperative Oncology Group. Am J Clin Oncol 5:649-655, 1982.* The Eastern Cooperative Oncology Group, Robert Comis M.D., Group Chair.

## 11.5 Multiple Myeloma Disease Response Criteria

Durie et al. International uniform response criteria for multiple myeloma. Leukemia. 2006; 20:1467-1473.

Criteria for multiple myeloma disease assessment:

**Table 5** International Myeloma Working Group uniform response criteria: CR and other response categories

Response subcategory	Response criteria a
sCR	CR as defined below plus Normal FLC ratio and Absence of clonal cells in bone marrow b by immunohistochemistry or immunofluorescence c
CR	Negative immunofixation on the serum and urine and Disappearance of any soft tissue plasmacytomas and ≤5% plasma cells in bone marrow b
VGPR	Serum and urine M-protein detectable by immunofixation but not on electrophoresis or 90% or greater reduction in serum M-protein plus urine M-protein level <100 mg per 24 h
PR	≥50% reduction of serum M-protein and reduction in 24-h urinary M-protein by ≥90% or to <200 mg per 24 h If the serum and urine M-protein are unmeasurable, d a ≥50% decrease in the difference between involved and uninvolved FLC levels is required in place of the M-protein criteria. If serum and urine M-protein are unmeasurable, and serum free light assay is also unmeasurable, ≥50% reduction in plasma cells is required in place of M-protein, provided baseline bone marrow plasma cell percentage was ≥30% In addition to the above listed criteria, if present at baseline, a ≥50% reduction in the size of soft tissue plasmacytomas is also required
SD (not recommended for use as an indicator of response; stability of disease is best described by providing the time to progression estimates)	Not meeting criteria for CR, VGPR, PR or progressive disease

Abbreviations: CR, complete response; FLC, free light chain; PR, partial response; SD, stable disease; sCR, stringent complete response; VGPR, very good partial response.

aAll response categories require two consecutive assessments made at anytime before the institution of any new therapy; all categories also require no known evidence of progressive or new bone lesions if radiographic studies were performed. Radiographic studies are not required to satisfy these response requirements.

bConfirmation with repeat bone marrow biopsy not needed.

cPresence/absence of clonal cells is based upon the  $k/\lambda$  ratio. An abnormal  $k/\lambda$  ratio by immunohistochemistry and/or immunofluorescence requires a minimum of 100 plasma cells for analysis. An abnormal ratio reflecting presence of an abnormal clone is  $k/\lambda$  of >4:1 or <1:2.

dRefer to Table 4 for definitions of measurable disease.

**Table 6** International Myeloma Working Group uniform response criteria: disease progression and relapse

Relapse subcategory	Relapse criteria
Progressive disease a To be used for calculation of time to progression and progression-free survival end points for all patients including those in CR (includes primary progressive disease and disease progression on or off therapy)	Progressive Disease: requires any one or more of the following: Increase of ≥25% from baseline in Serum M-component and/or (the absolute increase must be ≥0.5 g/dl) b Urine M-component and/or (the absolute increase must be ≥200 mg/24 h) Only in patients without measurable serum and urine M-protein levels: the difference between involved and uninvolved FLC levels. The absolute increase must be >10 mg/dl. Bone marrow plasma cell percentage: the absolute % must be ≥10% c Definite development of new bone lesions or soft tissue plasmacytomas or definite increase in the size of existing bone lesions or soft tissue plasmacytomas Development of hypercalcemia (corrected serum calcium >11.5 mg/dl or 2.65 mmol/l) that can be attributed solely to the plasma cell proliferative disorder
Clinical relapse d	Clinical relapse requires one or more of: Direct indicators of increasing disease and/or end organ dysfunction (CRAB features) b It is not used in calculation of time to progression or progression-free survival but is listed here as something that can be reported optionally or for use in clinical practice 1. Development of new soft tissue plasmacytomas or bone lesions 2. Definite increase in the size of existing plasmacytomas or bone lesions. A definite increase is defined as a 50% (and at least 1 cm) increase as measured serially by the sum of the products of the cross-diameters of the measurable lesion 3. Hypercalcemia (>11.5 mg/dl) [2.65 mmol/l] 4. Decrease in hemoglobin of ≥2 g/dl [1.25 mmol/l] (see Table 3 for further details) 5. Rise in serum creatinine by 2 mg/dl or more [177 μmol/l or more]
Relapse from CR e (To be used only if the end point studied is DFS) d	Any one or more of the following: Reappearance of serum or urine M-protein by immunofixation or electrophoresis Development of ≥5% plasma cells in the bone marrow c Appearance of any other sign of progression (i.e., new plasmacytoma, lytic bone lesion, or hypercalcemia see below)

Abbreviations: CR, complete response; DFS, disease-free survival.

aAll relapse categories require two consecutive assessments made at anytime before classification as relapse or disease progression and/or the  
institution of any new therapy.

bFor progressive disease, serum M-component increases of ≥1 gm/dl are sufficient to define relapse if starting M-component is ≥5 g/dl.

cRelapse from CR has the 5% cutoff versus 10% for other categories of relapse.

dFor purposes of calculating time to progression and progression-free survival, CR patients should also be evaluated using criteria listed above for  
progressive disease.

**11.6 Events of Clinical  
Interest  
Reference Table**

Pneumonitis (reported as ECI if <math>\geq</math> Grade 2)		
Acute interstitial pneumonitis	Interstitial lung disease	Pneumonitis
Colitis (reported as ECI if <math>\geq</math> Grade 2 or any grade resulting in dose modification or use of systemic steroids to treat the AE)		
Intestinal Obstruction	Colitis	Colitis microscopic
Enterocolitis	Enterocolitis hemorrhagic	Gastrointestinal perforation
Necrotizing colitis	Diarrhea	
Endocrine (reported as ECI if <math>\geq</math> Grade 3 or <math>\geq</math> Grade 2 and resulting in dose modification or use of systemic steroids to treat the AE)		
Adrenal Insufficiency	Hyperthyroidism	Hypophysitis
Hypopituitarism	Hypothyroidism	Thyroid disorder
Thyroiditis	Hyperglycemia, if $\geq$ Grade 3 and associated with ketosis or metabolic acidosis (DKA)	
Endocrine (reported as ECI)		
Type 1 diabetes mellitus (if new onset)		
Hematologic (reported as ECI if <math>\geq</math> Grade 3 or any grade resulting in dose modification or use of systemic steroids to treat the AE)		
Autoimmune hemolytic anemia	Aplastic anemia	Thrombotic Thrombocytopenic Purpura (TTP)
Idiopathic (or immune) Thrombocytopenia Purpura (ITP)	Disseminated Intravascular Coagulation (DIC)	Haemolytic Uraemic Syndrome (HUS)
Any Grade 4 anemia regardless of underlying mechanism		
Hepatic (reported as ECI if <math>\geq</math> Grade 2, or any grade resulting in dose modification or use of systemic steroids to treat the AE)		
Hepatitis	Autoimmune hepatitis	Transaminase elevations (ALT and/or AST)
Infusion Reactions (reported as ECI for any grade)		
Allergic reaction	Anaphylaxis	Cytokine release syndrome
Serum sickness	Infusion reactions	Infusion-like reactions
Neurologic (reported as ECI for any grade)		
Autoimmune neuropathy	Guillain-Barre syndrome	Demyelinating polyneuropathy
Myasthenic syndrome		
Ocular (report as ECI if <math>\geq</math> Grade 2 or any grade resulting in dose modification or use of systemic steroids to treat the AE)		
Uveitis	Iritis	
Renal (reported as ECI if <math>\geq</math> Grade 2)		
Nephritis	Nephritis autoimmune	Renal Failure
Renal failure acute	Creatinine elevations (report as ECI if $\geq$ Grade 3 or any grade resulting in dose modification or use of systemic steroids to treat the AE)	
Skin (reported as ECI for any grade)		
Dermatitis exfoliative	Erythema multiforme	Stevens-Johnson syndrome
Toxic epidermal necrolysis		
Skin (reported as ECI if <math>\geq</math> Grade 3)		
Pruritus	Rash	Rash generalized
Rash maculo-papular		
Any rash considered clinically significant in the physician's judgment		
Other (reported as ECI for any grade)		
Myocarditis	Pancreatitis	Pericarditis
Any other Grade 3 event which is considered immune-related by the physician		

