#### 4.1.2 Subject Inclusion Criteria

In order to be eligible for participation in this trial, the subject must:

1. Be willing and able to provide written informed consent/assent for the trial.
2. Be  $\geq 18$  years of age on day of signing informed consent.
3. Has a confirmed diagnosis of MM based on standard criteria. (See Appendix 2 for MM Diagnostic Criteria.)

4. Is between 60 and 180 days from peripheral blood autologous stem cell transplant.

5. At diagnosis, had MM with measurable disease, defined as:

- A monoclonal immunoglobulin spike on serum electrophoresis of at least 0.5 g/dL and/or
- Urine monoclonal levels of at least 200 mg/24 hours
- For subjects without measurable serum and urine M-protein levels, an abnormal free light chain (FLC) ratio (normal value 0.26 – 1.65) with involved FLC  $\geq 10$  mg/dL
- Radiographic evidence of disease for those without measurable M-spike or free light chains.

6. Has high-risk MM, which must be present at the time of diagnosis, and defined by:

- a. International Staging System (ISS) stage 3 (See Appendix 3 for ISS Staging), and/or
- b. Deletion 13q by cytogenetics, and/or
- c. 1q amplification, 1p deletion, p53 deletions (17p deletions), t(4;14), t(14;16), t(14;20), hypodiploidy, and/or
- d. High-risk gene expression profile (GEP) scores

7. Be able to provide a newly obtained bone marrow aspirate/biopsy material for biomarker analysis and disease assessment.

8. Have a performance status of  $\leq 2$  on the ECOG Performance Scale (See Appendix 4).

9. Demonstrate adequate organ function as defined in Table 1, all screening labs should be performed within 28 days of treatment initiation.

Table 1 Adequate Organ Function Laboratory Values

System	Laboratory Value
Hematological	
Absolute neutrophil count (ANC)	$\geq 1,000$ /mcL
Platelets	$\geq 75,000$ / mcL
Hemoglobin	$\geq 8$ g/dL or $\geq 5.6$ mmol/L without transfusion or EPO dependency (within 7 days of assessment)
Renal	
Serum creatinine OR Measured or calculated a creatinine clearance (GFR can also be used in place of creatinine or CrCl)	$\leq 1.5$ X upper limit of normal (ULN) OR $\geq 60$ mL/min for subject with creatinine levels $> 1.5$ X institutional ULN
Hepatic	

Serum total bilirubin	
	$\leq 1.5 \times \text{ULN}$ OR
	Direct bilirubin $\leq \text{ULN}$ for subjects with total bilirubin levels $> 1.5 \text{ ULN}$
AST (SGOT) and ALT (SGPT)	

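### The CR and VGPR rows of the response table have no free-light-chain condition, so a patient measurable only by serum FLC can score CR while failing PR

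*Combined protocol and SAP*

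**What the plan says.** Inclusion criterion 5 (section 4.1.2) requires measurable disease at diagnosis. One of its routes is "For subjects without measurable serum and urine M-protein levels, an abnormal free light chain (FLC) ratio", with involved FLC of at least 10 mg/dL. The trial therefore admits patients whose only measurable marker is serum FLC.

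The response tables in Appendix 11.5 treat FLC unevenly:

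- **sCR:** "CR as defined below plus Normal FLC ratio and Absence of clonal cells in bone marrow". This is the only complete-response category with an FLC term.
- **CR:** "Negative immunofixation on the serum and urine and Disappearance of any soft tissue plasmacytomas and ≤5% plasma cells in bone marrow". No FLC term.
- **VGPR:** "Serum and urine M-protein detectable by immunofixation but not on electrophoresis", or a 90% fall in serum M-protein with low urine M-protein. No FLC alternative.
- **PR:** when serum and urine M-protein are unmeasurable, "a ≥50% decrease in the difference between involved and uninvolved FLC levels is required in place of the M-protein criteria".
- **PD:** "Only in patients without measurable serum and urine M-protein levels: the difference between involved and uninvolved FLC levels" must rise by at least 25% from baseline and by more than 10 mg/dL.

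A footnote on who counts as measurable says "Refer to Table 4 for definitions of measurable disease", but Appendix 11.5 contains no such table. Another footnote says that, for calculating TTP and PFS, "CR patients should also be evaluated using criteria listed above for" progressive disease.

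Section 7.1.6.1 counts any sCR, CR, VGPR or PR towards ORR, and scores response from two baselines: before ASCT, and cycle 1 day 1 or screening. Sections 7.1.1 and 7.1.8.1 give both response rates an exact binomial analysis in the full analysis set (FAS). Section 7.1.7.1 bases duration of response (DOR) on all responders.

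**The concern.** Response categories should be ordered, so that a patient in a deeper category has also cleared the shallower ones. For FLC-only patients the table breaks that order. PR demands a halving of the FLC difference. CR demands nothing of FLC, and section 7.1.6.1 does not make CR conditional on meeting PR.

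The trial's timing makes this more than a curiosity. Patients enter 60 to 180 days after ASCT, so an FLC-only patient may already be immunofixation-negative with few marrow plasma cells at cycle 1 day 1. That patient can score CR with no change in the one marker that shows the disease. The requirement for two consecutive assessments does not screen this out, because the state persists and a footnote waives repeat marrow confirmation.

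At stake are the CR+sCR+VGPR rate, ORR and membership of the DOR set, in a single-arm trial with investigator-assessed response.

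**Working it through.** **1. The plan's own figure.** The only design calculation is the Simon two-stage design for 12-month PFS in section 7.1.3 (50% versus 70%; continue if more than 8 of 15; succeed if more than 26 of 43).

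- Probability of early termination = P(X ≤ 8 | n = 15, p = 0.50) = 0.6964.
- Expected size = 15 + 28 × (1 − 0.6964) = 23.5.
- Exact type I error 0.0499; power 0.804.

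These reproduce the plan. They supply the denominator of 43 and are not in question. No target or historical value is stated for either response rate.

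**2. The rules applied to one type of patient.** Take serum and urine M-protein unmeasurable, immunofixation negative, marrow plasma cells 4%, no plasmacytoma and an abnormal FLC ratio (so not sCR). PR needs follow-up ≤ 0.5 × baseline. PD needs follow-up ≥ 1.25 × baseline and a rise > 10 mg/dL.

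| FLC difference, mg/dL | Change | CR | PR | PD |
|---|---|---|---|---|
| 20 → 18 | −10% | yes | no | no |
| 12 → 4 | −67% | yes | yes | no |
| 12 → 8 | −33% | yes | no | no |
| 12 → 12 | 0 | yes | no | no |
| 12 → 22 | +83%, +10 | yes | no | no |
| 12 → 22.5 | +87.5%, +10.5 | yes | no | yes |
| 12 → 30 | +150%, +18 | yes | no | yes |

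The CR column never changes, because FLC is not in the CR rule.

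**3. Where PD takes over.** Below a baseline of 40 mg/dL (25% of 40 = 10) the absolute condition binds, so any rise up to 10 mg/dL leaves the patient a CR. In the last two rows, once confirmed, the patient is a progressor for PFS and TTP. The CR row does not exclude PD, as the SD row does, and the footnote on CR patients covers only TTP and PFS. Which label wins for the response rate is unstated.

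**4. VGPR.** The missing FLC branch works both ways. A patient with M-protein visible only on immunofixation is VGPR whatever FLC does. A patient with a 90% fall in the FLC difference, negative immunofixation and marrow above 5% scores only PR.

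**5. Size.** Each false CR adds 1/FAS size to both rates. With a FAS of 43 and k false CRs (k is an assumption; the documents give no count):

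| k | Added points (k/43) |
|---|---|
| 1 | 2.3 |
| 2 | 4.7 |
| 4 | 9.3 |

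For illustration, if the true count were 22 of 43 (51.2%, exact 90% CI 37.7 to 64.5), two false CRs would give 24 of 43 (55.8%, 42.2 to 68.8). If the trial stopped after stage one, each would add 1/15 = 6.7 points.

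**The case against.** The strongest reply is that the table is a published standard used unmodified, and that Appendix 11.5 is an excerpt: the table on measurable disease is absent, so the source might contain a rule for FLC-only patients. Using a standard also keeps the rate comparable with history. The comparability point stands as a cost. The rest does not remove the gap. Sections 3.2.3.1, 6.1.2.7.2, 7.1.6.1 and 7.1.8.1 add no FLC condition, and the trial scores its patients on the rows that it reproduces.

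The reply is right that several stronger inferences fail:

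- **That progressing patients escape as CR.** Confirmed PD is still counted for PFS and TTP. Only its precedence in the response rate is unstated.
- **That every FLC-only patient is exposed.** M-protein below the measurable limit is not the same as negative immunofixation, and measurability in criterion 5 is judged at diagnosis. A false CR needs FLC-only disease, negative serum and urine immunofixation, marrow ≤5%, no plasmacytoma, a persisting FLC difference with less than a 50% fall, no PD at screening and two assessments. A light-chain patient with measurable urine M-protein who becomes immunofixation-negative also meets the urine part of PR.
- **That the inflation has a known size.** It does not; any share of affected patients is assumed.
- **That the biomarker comparisons are broadly contaminated.** Section 7.1.8.3 pools short responders with non-responders, so a false CR who soon progresses stays in the same group.

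Consistent follow-up of the Primary Myeloma Panel (section 6.1.2.7.1) helps with data capture but adds no scoring rule.

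**Conclusion.** The table is wrong as written for patients measurable only by serum FLC. They can be CR, and count in CR+sCR+VGPR, ORR and the DOR set, with an FLC difference that is unchanged or has risen short of PD. The CR error can only raise the rates: 2.3 points per patient with a FAS of 43, or 4.7 points if two patients were affected. The count is an assumption and may be small. The VGPR gap can move the CR+sCR+VGPR rate in either direction.

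A reader might infer that the primary result is at risk. The documents do not support that: PD has an FLC branch, the go/no-go rule rests on 12-month PFS, and the Simon figures reproduce. The effect on the response-rate p-values cannot be calculated, because no historical rate is stated. This should be corrected, but it affects secondary endpoints only.

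**What to change.** In Appendix 11.5 and section 7.1.6.1, for patients whose only measurable disease at the response baseline is serum FLC:

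1. Require a normal FLC ratio for CR, in addition to the existing CR criteria.
2. Add an FLC-difference criterion for VGPR that is stricter than the one for PR. A fall of at least 90% would mirror the serum M-protein figure already in the VGPR row.

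For all patients:

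3. State that a visit meeting PD cannot count as a response.
4. Insert the missing definition of measurable disease, and say at which of the two response baselines it is judged.

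Do not go further and score patients with no measurable M-protein or FLC as automatic non-responders. Under the cycle 1 day 1 baseline that would turn true post-transplant remissions into non-response, and it would bar CR for the patients whom criterion 5 admits on radiographic evidence alone.

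The cost is wording. Section 5.1 already schedules FLC on day 1 of each cycle, at end of treatment and at follow-up visits. The response rate may be slightly lower, and slightly less comparable with a historical rate scored on the unmodified table. Reporting the rate both ways would show the difference. The PD row and the primary analysis do not change.
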